#### Death rate (secondary outcome)

In case of non-response of participants to the post-test questionnaires, it will be investigated by means of the computerized patient record of the hospital or with the relatives or the attending physicians in charge of the participants if the participants died within one month of the hospital discharge.

#### Assessment of satisfaction (secondary outcome)

Satisfaction with the teaching interview will be assessed by means of a questionnaire that the patient will complete directly after the teaching interview (Appendix 5).

Overall satisfaction with the pharmacist's care will be assessed at 1 month post discharge. They will be evaluated only in the intervention group

The questionnaire will be sent to the patient by email or regular mail. If no return is obtained, the research assistant will address the questionnaires to them during a telephone call (Appendix 6).

#### Evaluation of the patient's experience and feelings upon return home (secondary outcome)

The patient's experience and feelings on returning home will be evaluated for the intervention group during a telephone call between D3 and D7 of the hospital discharge by the investigating pharmacist using a questionnaire sent by the investigating pharmacist (Appendix 7)

#### Use of the electronic treatment plan (secondary outcome)

Patients who were presented with and installed the CardioMeds mobile application® during hospitalization will be asked if they used it and if they were satisfied with it. It will be the research assistant who will collect these elements during the telephone call at 1 month post hospital discharge using a validated standardized questionnaire (Appendix 9). In addition, as the mobile application is specifically designed to empower the patient in his care, a validated standardized self-care questionnaire will also be filled out on this occasion (Appendix 10).

#### *Other item evaluated*

The participant will be asked during the 1-month telephone call if he/she has entered a specific cardiac rehabilitation program for heart failure. He/she will also be asked to provide his/her last medication list to analyze if there have been any changes in the treatment of heart failure since discharge.

#### **4.4 Withdrawal and interruption**

A participant may withdraw from the study at any time if he or she no longer wishes to participate. A participant will be withdrawn from the study if he/she dies, if his/her health condition deteriorates to the point where he/she can no longer meet the inclusion criteria or be physically able to follow the pharmacist's intervention, if he/she loses his/her capacity of discernment, if he/she cannot be reached by telephone after discharge from the hospital.

A study with temporal follow-up is associated with a significant risk of break in follow-up or

withdrawal of informed consent. Therefore, we choose to implement an intention-to-treat analysis. The data collected will be retained until the loss of a participant. The number of lost to follow-up will be specified in the results in the form of a flowchart. All data used in the analysis will be anonymized afterwards.

## **5 STATISTICS AND METHODOLOGY**

This chapter of the protocol describes the research hypotheses, statistical analysis plan, sample size, and treatment of missing data.

It was submitted to [name], head of the methodological support unit of the HUG clinical research center, who assisted us in the construction of these elements and their validation.

The final analysis will be based on the intention-to-treat principle, i.e. including all patients who were randomized in the study.

For the basic data, continuous variables will be described as means and standard deviation, median and inter-quartile range.

The discrete or categorical variables will be described by their numbers and relative proportion, or even the mean and standard deviation, depending on the variables

Some continuous data such as age, left ventricular ejection fraction (LVEF), laboratory data, length of hospital stay, number of pre- and post-hospitalization medications will be reclassified into categories and presented as numbers and relative proportion of each category. Differences in outcomes between the intervention and control groups will be analyzed using the t-test for continuous variables and a Chi-Square test for categorical variables.

The main analysis assessing knowledge status will compare the knowledge score (dependent variable) between the two randomization groups (main independent variable) after adjusting for knowledge status at baseline using a linear regression model or ANCOVA.

For continuous secondary outcomes (medication beliefs and medication adherence), a Student's t test will also be used to compare mean values between the two groups. For binary outcomes (re-hospitalization or new emergency department visit within 1 month), a chi-2 test (or Fisher exact test if the smallest expected number of patients is <5) will be used.

For the satisfaction outcome, which is an ordinal qualitative variable, a Chi-2 test (or Fisher's exact test if the smallest expected number of participants is <5) will be used.

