 28 For example for question n° 2: 1 point if predefined keyword present; 0,5pt if partial keyword  
 29 but general concept correct; 0 pt otherwise.

30  
 31 The final score can vary from 0 (no knowledge) to 17 points (excellent knowledge).  
 32 The questionnaire has never been used in an experimental context or for psychometric  
 33 analysis. There is no threshold to say that a patient has good knowledge or not.  
 34 It was developed by an internal pharmacist and an assistant pharmacist trained in TVE. It is  
 35 based on educational objectives derived from educational sessions with patients and meetings  
 36 with two patient partners from the HUG (Appendix 2). It was previously evaluated with them  
 37 and on three occasions with a group of hospitalized heart failure patients (10 patients per  
 38 version of the questionnaire).

39  
 40 To determine a first basic level of knowledge of the heart failure patients hospitalized at the  
 41 HUG, the final version of the questionnaire was tested with 10 patients who had not received  
 42 any educational intervention. This analysis shows that:

- 43 • The average baseline score is 7.95 pts out of 17.00pts (with a standard deviation of  
 44 2.67) or 46.76% of correct answers;
- 45 • The median score of 8.25pts out of 17.00 pts (min. 4; max. 13) or 48.53% of correct  
 46 answers.

47  
 48 In this clinical study, we wish to assess the level of knowledge of the intervention group before  
 49 the teaching interview, directly after the teaching interview, and at 1 month after the  
 50 participant's discharge from the hospital.

51 This study includes a control group in order to evaluate the real effect of the therapeutic  
 52 teaching intervention. The level of knowledge of the control group will be evaluated at inclusion  
 53 for the pre-test and at 1 month after hospitalization for the post-test.

54

1  
2 Secondary endpoints included differences in medication belief and adherence scores and the  
3 difference in the rate of unplanned care use between the two groups at 1 month post-  
4 hospitalization.

5  
6 They also focused, for the intervention group, on the difference in belief and therapeutic  
7 adherence scores between the period before the educational intervention during  
8 hospitalization and the period following this intervention, i.e., one month after hospital  
9 discharge.

10 Four additional endpoints will be assessed after the pharmaceutical intervention with the study  

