#### Assessment of beliefs about medications (secondary outcome)

Beliefs about medicines will be assessed indirectly using the Beliefs about Medicines Questionnaire (Appendix 3) at time 0 (pre-test) after obtaining the consent form and at 1 month after hospitalization (post-test) in both groups.

During hospitalization, the questionnaire will be sent to the patient by the investigating pharmacist and it will be filled in by the patient himself with the help of the pharmacist if necessary. One month after discharge, the questionnaire will be sent to the patient by email or post. If no return is obtained, the research assistant will send them the questionnaires during a telephone call.

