#### Assessment of therapeutic adherence (secondary outcome)

Adherence to therapy will be assessed for all participants with the 3-item self-report questionnaire (Appendix 4) on two occasions. It will be presented to the participant by the investigator at time 0 after obtaining the consent form (pre-test), as well as at 1 month post-hospitalization. During hospitalization, the questionnaire will be sent to the patient by the investigating pharmacist and completed by the patient himself with the help of the pharmacist if necessary.

At 1 month after discharge, the questionnaire will be sent to the patient by email or post. If no return is obtained, the research assistant will address the questionnaires to them during a phone call.

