## Secondary analyses

Comparisons of continuous secondary outcomes between the two randomization groups will be made by Student's t tests; comparisons of categorical or ordinal qualitative secondary outcomes will be made using a Chi-2 test or Fisher's exact test (in case of smaller expected number <5). The analyses will be carried out by a statistician from the methodological support unit of the HUG clinical research center on a specific and recognized computer software.

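### Beliefs and adherence are compared at 1 month by unadjusted t tests although both are measured at baseline in both arms, which gives up precision and leaves chance imbalance uncorrected.

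*Combined protocol and SAP*

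**What the plan says.** Three places name the test for these outcomes: the synopsis (statistical considerations), section 5, and the secondary analyses in section 5.1. Section 5 says that a Student's "t test will also be used to compare mean values between the two groups". Section 5.1 reads: "Comparisons of continuous secondary outcomes between the two randomization groups will be made by Student's t tests". None mentions a covariate. Section 3.2 places the between-group comparison of belief and adherence scores at 1 month after hospitalization.

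Both scales have a baseline in both arms. Section 4.3 has beliefs assessed "at time 0 (pre-test) after obtaining the consent form and at 1 month after hospitalization (post-test) in both groups". On adherence it states: "Adherence to therapy will be assessed for all participants with the 3-item self-report questionnaire (Appendix 4) on two occasions", and places these "at time 0 after obtaining the consent form (pre-test), as well as at 1 month post-hospitalization". The resulting pre-test scores are items 57 to 62 of Table 2. Their only other stated analytic use is a before/after comparison within the intervention group (section 3.2).

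For the primary outcome, sections 5 and 5.1 specify a linear regression or ANCOVA of the 1-month knowledge score on arm, adjusted for the baseline knowledge score. No reason is given for treating the secondary scores differently.

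**The concern.** Beliefs and adherence are the main secondary questions. In the background section they are part of the route by which better knowledge is expected to improve treatment and reduce unplanned care. The trial was sized on the knowledge score alone, so precision on these scales depends on how well the analysis uses the data.

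A t test on 1-month scores leaves in the error term all the between-patient variation that the baseline could explain. Section 4.2 describes randomization in blocks of random size and states no stratification factor, so neither the design nor the analysis limits chance differences between arms on these scales. A null result could then reflect a wide interval, and a positive one could partly reflect where the arms started. The before/after comparison in the intervention group does not help, because it has no control.

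**Working it through.** **The plan's own figures.** The documents give no power or sample size for beliefs or adherence. The 40 per group in section 5.1 is for knowledge. It does not follow from the stated difference of 2.39 and SD of 2.67, which give 20 to 21 per group. It does follow from an SD of 2.67 × √2 = 3.78, which the plan does not state. This point does not depend on that; only the group sizes are used here.

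**Inputs.**
- Patients per group (section 5.1): 45 (planned enrolment), 40 (after 10% loss) and 62 (expected enrolment).
- Two-sided alpha of 5% (section 5.1).
- Correlation r between baseline and 1-month score: not in the documents; 0.3, 0.5 and 0.7 assumed.
- True effect: 0.5 SD, for illustration only.

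**Step 1: variance.** ANCOVA multiplies the variance of the group difference by 1 − r². The same precision from a t test would need 1/(1 − r²) times as many patients. The confidence interval width is multiplied by √(1 − r²).

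| r | Variance factor | Interval width factor | Equivalent sample multiplier |
|---|---|---|---|
| 0.3 | 0.91 | 0.95 | 1.10 |
| 0.5 | 0.75 | 0.87 | 1.33 |
| 0.7 | 0.51 | 0.71 | 1.96 |

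**Step 2: power.** Two-sample t power with standardized effect 0.5/√(1 − r²). The one model degree of freedom is ignored.

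| Per group | t test | ANCOVA, r = 0.3 | r = 0.5 | r = 0.7 |
|---|---|---|---|---|
| 40 | 60% | 64% | 72% | 87% |
| 45 | 65% | 69% | 77% | 91% |
| 62 | 79% | 83% | 89% | 97% |

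**Step 3: chance imbalance.** At 45 per group the difference in baseline means has an SD of √(2/45) = 0.21 in SD units. A baseline difference of b SD shifts the unadjusted 1-month difference by r × b. A difference beyond 0.4 SD in either direction has a probability of about 6%. If b is 0.4 and r is 0.5, the shift is 0.5 × 0.4 = 0.20 SD, and the type I error of the t test, given that imbalance, is about 12% instead of 5%.

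**Step 4: the other reading.** Sections 5 and 5.1 do not say whether the means are 1-month scores or changes. Section 3.2 points to 1-month scores. If changes were meant, the variance factor would be 2(1 − r): 1.4, 1.0 and 0.6 for the three correlations. That is worse than the plain t test below r = 0.5, and in each case above the ANCOVA factor.

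**The case against.** The strongest reply is that nothing planned is invalid. Over repeated randomization the t test is unbiased and holds its alpha, and its standard error already allows for chance imbalance. That stands: the loss is in precision and in error conditional on an observed imbalance.

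The gain is also uncertain. Baseline adherence refers to the period around admission and 1-month adherence to a discharge regimen that may differ, so r may be low for that scale. At r = 0.3 the gain is about 4 percentage points of power. This limits the size claimed, but not its direction, which is the same at 40, 45 and 62 per group.

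The most substantive point is timing. Section 4.3 has the pre-test collected after randomization, and the investigating pharmacist, who also delivers the intervention, may help patients complete it. If knowing the allocation moved the intervention arm's baseline answers by k SD, ANCOVA would shift the estimate by about −r × k. With k = 0.2 and r = 0.5 (both assumed) that is −0.1 SD, and a t test on 1-month scores would not be affected. However, the pre-test precedes the teaching, and the primary ANCOVA accepts the same timing. This is a reason to keep the t test as a sensitivity analysis, but not to make it the main one.

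Finally, it is not certain that baseline adherence is undefined for newly diagnosed patients. Section 3.2 describes the scale as asking about forgotten medication in the last month, without restricting it to heart failure drugs, and the wording in Appendix 4 was not available. Table 2 does allow a new diagnosis (item 32), no medication before admission (item 46) and no heart failure medication (item 47), so a rule is needed in case such patients occur.

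**Conclusion.** The point holds. Baselines of the same scales exist in both arms and are left out of the between-group analysis, while the primary outcome's model uses its own. This is a weakness of efficiency and consistency in secondary outcomes that should be corrected; it does not make the planned tests invalid. Adjustment lowers the variance by 9% to 51% for r between 0.3 and 0.7, equivalent to 10% to 96% more patients. That range rests on assumed correlations, and the power figures also rest on an illustrative effect of 0.5 SD. Apart from one degree of freedom, ANCOVA is no less efficient than either t test.

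**What to change.** In the synopsis, section 5 and the secondary analyses of section 5.1, replace the t tests for BMQ necessity, concerns, the differential and adherence with the model used for knowledge: 1-month score on arm plus the baseline of the same scale. Report the adjusted difference with its 95% confidence interval. Keep the unadjusted t test on 1-month scores as a sensitivity analysis; it also shows whether the post-randomization timing of the pre-test matters.

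State a rule for patients whose baseline adherence cannot be scored because they had no treatment in the prior month: include a missing-baseline indicator so that no one is dropped.

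The cost is SAP wording, one model degree of freedom (a second where the indicator is needed) and the missing-baseline rule. The data are already in Table 2. The change should be made before outcome data are analysed, so that the model is not chosen after seeing results.

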### **5.1 Statistical analysis plan and sample size calculation**

#### **Research Hypotheses**

The hypothesis of this project is that patients with heart failure who have received an educational interview combined with follow-up by the hospital pharmacist show an increase in their knowledge score after the intervention compared with the control group at 1 month after hospital discharge.

The null hypothesis is that there is no improvement in the knowledge score at 1 month after hospital discharge.

This hypothesis leads us to evaluate the primary endpoint: the improvement of knowledge about heart failure and its medications at 1 month after hospital discharge of patients hospitalized for

cardiac decompensation.

### **Sample size**

To test our hypothesis, we need to define an adequate sample size.

To do this, we initially consulted the literature. Several studies have demonstrated an improvement in patient knowledge after pharmacist intervention with approximately 100-200 patients (45–56).

The questionnaire used to measure patient knowledge has never been studied to date. We tested it in 10 hospitalized heart failure patients who were naïve to any teaching intervention.

This analysis shows that:

- The average baseline score is 7.95 pts out of 17.00pts (with a standard deviation of 2.67), i.e. 46.7% of correct answers;
- The median score of 8.25pts out of 17.00 pts (min. 4; max. 13) is 48.5% correct answers.

By setting a relative gain of 30% as the smallest difference to be detected, this would be equivalent to showing an improvement in the mean score of at least 2.39 points ( $\pm 7.01$ ) (i.e., a mean score increase from 7.95 to 10.34pts).

Assuming a two-sided alpha of 5% and a power of 80%, 40 subjects per group should be included, for a total of 80 subjects. Considering a loss to follow-up in about 10% of the study subjects, the required sample size would be at least 90 subjects (45 subjects per group). This sample size was calculated with STATA 17 (STATA Corporation, College Station, Texas).

We also need to consider the average number of patients hospitalized at the HUG for left heart decompensation with decreased LVEF to define the inclusion time and feasibility of this project. Note that according to internal hospital statistics, the number of patients hospitalized in general internal medicine for left heart decompensation (all severities and LVEFs combined) in 2019 was 641 and 434 between January and November 2021. It is considered that 50% of these patients have a reduced LVEF, equivalent to 200-330 patients per year who could benefit from our intervention or approximately 16-25 patients per month. A certain number of these patients will not meet the inclusion criteria and a small number, approximately 30%, will agree to participate, as shown by certain studies in heart failure patients (71–74). In addition, some patients will be missed by the investigator who will only work part-time on this project.

Based on all these elements, we expect to include approximately 124 patients (62 per group) over 12 months, to show a progression of knowledge which is a sufficient number to guarantee the statistical power of the study.

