Number of participants with rationale	
The mean knowledge score found in heart failure patients hospitalized at the HUG and naïve to any educational program was 7.95 points out of 17 points, with a standard deviation of 2.67. A 30% difference in score improvement was chosen as the smallest

	
difference to be detected with clinical significance (i.e., a score difference of 2.39) to be detected. Assuming a study power of 80% and an alpha error of 5% (two-sided), it would be necessary to recruit a total of 80 patients (40 per group) to be able to detect such a difference between the two groups. We anticipate 10% loss to follow-up, which leads to a sample size of 90 subjects in total, or 45 per group. This sample size was calculated with STATA 17 (STATA Corporation, College Station, Texas).
 
We expect to include approximately 124 patients during the 12-month inclusion period. Indeed, 200-300 patients are hospitalized annually at the HUG in the Department of General Internal Medicine or Cardiology for heart failure with reduced LVEF, i.e., about 16-25 patients per month. Taking into account refusals to participate and patients we will not have time to include, we think we can reach 62 patients per group.

Study Intervention	
The intervention by a clinical pharmacist includes
 
 
- Targeted education on patient needs related to heart failure, heart failure medications and self-care;
 
- a pre-discharge interview to consolidate key teaching messages and prepare the patient for their discharge treatment plan;
 
- a telephone call the week of discharge to ensure pharmaceutical follow-up between hospital care and return home (continuity of care).
 

Control Intervention	
Hospitalized heart failure patients with reduced or mildly reduced LVEF who do not benefit from the pharmacist's educational intervention but do benefit from the usual standard of care.

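### The expected 124 inclusions do not follow from the plan's printed pool and 30% acceptance, which give about 60-99 a year, so the implied margin over the required 90 is unsupported

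*Combined protocol and SAP*

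**What the plan says.** Section 5.1 (Sample size) requires 40 patients per group, raised to 45 per group (90 in total) for 10% loss to follow-up. It then turns to feasibility:

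- **Source counts.** General internal medicine admissions for left heart decompensation ("all severities and LVEFs combined) in 2019 was 641 and 434 between January and November 2021").
- **Reduced LVEF.** "It is considered that 50% of these patients have a reduced LVEF", which the plan treats as "equivalent to 200-330 patients per year who could benefit from our intervention or approximately 16-25 patients per month".
- **Losses.** "A certain number of these patients will not meet the inclusion criteria"; "a small number, approximately 30%, will agree to participate"; and "some patients will be missed by the investigator who will only work part-time on this project". Only the acceptance rate is given a number.
- **Conclusion.** On the strength of these elements, "we expect to include approximately 124 patients (62 per group) over 12 months". The plan calls this number enough to assure the study's power.

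The synopsis (Number of participants with rationale) repeats the figure: "we think we can reach 62 patients per group". Its pool is 200-300 a year, attributed to general internal medicine or cardiology, and it does not mention the 30%.

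**The concern.** The plan offers 124 as the product of a pool and a chain of reductions. One of those reductions, applied alone, already brings the pool below 124. A reader such as an ethics committee would take 124 against 90 as a margin of 34 patients. If the inputs do not supply that margin, the plan's own target of 90 may not be met in the planned 12 months, and the assurance about power has no basis. Section 6.5 lists insufficient recruitment among the reasons for early termination, so the projection matters.

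**Working it through.** **Step 1. Try to reproduce 124.** Expected inclusions = annual pool x acceptance, before ineligible and missed patients are removed.

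| Pool, and where it comes from | Patients per year | x 0.30 |
|---|---|---|
| Section 5.1, annual range | 200-330 | 60-99 |
| Section 5.1, 16-25 per month x 12 | 192-300 | 58-90 |
| Section 5.1, 2019 count: 641 x 0.5 | 320.5 | 96 |
| Section 5.1, 2021 count annualised: 434 x 12/11 x 0.5 | 237 | 71 |
| Synopsis, annual range | 200-300 | 60-90 |

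No row gives 124. It is 25% above the highest value (124/99 = 1.25) and about twice the lowest (124/60 = 2.07).

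**Step 2. What 124 would need.** At 30% acceptance, 124/0.30 = 413 patients a year, which is 83 more than the top of the printed range. With the printed pool, the share of all patients included would have to be 124/330 = 38% to 124/200 = 62%.

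**Step 3. Compare with the required 90.** The dropout step reproduces: 40/0.9 = 44.4, rounded up to 45 per group, or 90. At 30% acceptance, 90/0.30 = 300 patients a year with no other loss. Time to 90:

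- At 99 a year: 90/99 x 12 = 10.9 months.
- At 60 a year: 90/60 x 12 = 18 months.
- On the source counts: 90/96 x 12 = 11.2 months to 90/71 x 12 = 15.2 months.

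**Step 4. What a shortfall would do to power.** Two-sample t-test, two-sided alpha 0.05, difference 2.39 (30% of 7.95). The printed SD of 2.67 gives 21 per group at 80% power, not 40. Solving for the SD that gives 40 per group yields 3.77, close to 2.67 x √2 = 3.78. The plan does not state such an SD, so both values are shown.

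| Total randomised | Power, SD 2.67 | Power, SD 3.77 |
|---|---|---|
| 60 | 93% | 68% |
| 70 | 96% | 74% |
| 90 | 99% | 84% |
| 99 | 99% | 88% |
| 124 | over 99% | 94% |

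These figures take every randomised patient as evaluable and ignore the baseline adjustment in the primary analysis.

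**The case against.** **The pool may be larger than printed.** The counts in section 5.1 are for general internal medicine, while section 4.1 also recruits from cardiology and admits patients who decompensate during a stay for another reason. This stands: 60-99 is a limit on the printed pool, not on what the hospital could recruit. It does not rescue 124, because the synopsis attributes 200-300 to the two departments together and no separate cardiology count is given.

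**The low end may be too low.** The 2021 count annualises to 237 after halving, not 200. This also stands. The source counts support 71-96 rather than 60-99, which is still well short of 124.

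**The 30% may already be net of ineligibility.** The plan does not say whether it applies to all admissions or to eligible patients approached. If it is net, 60-99 is close to the estimate itself rather than an upper limit. For this reason no further eligibility fraction is applied here, since the documents give none.

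**Power may survive.** A reader might infer that the trial will be underpowered. The documents do not support that. With the only SD they print, 60 patients give about 93% power. The 68% depends on an SD back-solved from 40 per group. The baseline-adjusted primary analysis could raise it: at SD 3.77 and 30 per group, an assumed baseline correlation of 0.3, 0.5 or 0.6 gives about 72%, 80% or 86%. The plan states no correlation.

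**Twelve months is a plan, and 124 is labelled an expectation.** Both are true. Inclusion could be extended by amendment, and 90 is already the stated requirement. Neither point makes 124 follow from the inputs.

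**Conclusion.** The 124 is not derivable from the plan's printed inputs. They give 60-99 a year (71-96 from the source counts, 60-90 from the synopsis pool). Only a pool of at least 300 with no loss beyond non-acceptance reaches 90. The margin of 34 patients and the assurance about power are therefore unsupported, and what is at risk is the plan's own target of 90 within the planned 12 months.

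This rests on the pool as printed and on reading the 30% as a share of that pool. A reader might take 60-99 as a hard cap, but the documents do not settle the denominator. The effect on power cannot be settled either until the plan states the SD behind 40 per group. The endpoint, the primary analysis and the required number are unaffected. The mismatch between 330 a year (27.5 a month) and the printed upper figure of 25 a month is minor, but should be corrected at the same time.

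**What to change.** 1. In section 5.1 and the synopsis, give the pool separately for general internal medicine and cardiology, and make the two places agree.
2. State what the 30% applies to, and put a figure or a range on ineligible and missed patients.
3. Replace 124 (62 per group) in both places with the number these inputs give. On the printed pool that is about 60-99 a year.
4. Keep the existing target of 90. Either recruit until it is reached rather than closing at 12 months, or state the power at the expected 12-month number together with the SD used.
5. Delete the statement that the expected number assures the study's power.

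The cost is a less favourable accrual figure and possibly a longer inclusion period. The target does not rise.
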